6.3.6 Progression-Free Survival

PFS is defined as the duration of time from start of treatment to time of progression or death, whichever occurs first.

6.3.7 Immune-Related Response Criteria

As an exploratory endpoint antitumor activity will also be evaluated according to iRECIST. (3)

Using iRECIST criteria the following will be incorporated into assessment:

1. An increase in the sum of target lesions of more than 20%, unequivocal increase in non-target lesions or new lesions result in iUPD (unconfirmed progressive disease); iUPD can be assigned multiple times as long as iCPD (confirmed progressive disease) is not confirmed at the next assessment.
2. Progression is confirmed in the target lesion category if the next imaging assessment after iUPD (4–8 weeks later) confirms a further increase in sum of measures of target disease from iUPD, with an increase of at least 5 mm. Progression is confirmed in the non-target lesion category if subsequent imaging, done 4–8 weeks after iUPD, shows a further unequivocal increase in non-target lesions. Progression is confirmed in the new lesion category if at next assessment additional new lesions appear or an increase in size of previously seen new lesions is seen (≥ 5 mm for sum of new lesion target).
3. However, the criteria for iCPD (after iUPD) are not considered to have been met if complete response, partial response, or stable disease criteria (compared with baseline and as defined by RECIST 1.1) are met at the next assessment after iUPD. The status is reset (unlike RECIST 1.1, in which any progression precludes later complete response, partial response, or stable disease). iCR, iPR, or iSD should then be assigned; and if no change is detected, then the timepoint response is iUPD.

6.4 TOXICITY CRITERIA

The following adverse event management guidelines are intended to ensure the safety of each participant while on the study. The descriptions and grading scales found in the revised NCI Common Terminology Criteria for Adverse Events (CTCAE) version 5.0 will be utilized for AE reporting. All appropriate treatment areas should have access to a copy of the CTCAE version 5.0. A copy of the CTCAE version 5.0 can be downloaded from the CTEP web site (http://ctep.cancer.gov/protocolDevelopment/electronic_applications/ctc.htm).

7 NIH REPORTING REQUIREMENTS / DATA AND SAFETY MONITORING PLAN

7.1 DEFINITIONS

Please refer to definitions provided in Policy 801: Reporting Research Events found at: <https://irbo.nih.gov/confluence/pages/viewpage.action?pageId=36241835#Policies&Guidance-800Series-ComplianceandResearchEventReportingRequirements>.

7.2 OHSRP OFFICE OF COMPLIANCE AND TRAINING / IRB REPORTING

7.2.1 Expedited Reporting

Please refer to the reporting requirements in Policy 801: Reporting Research Events and Policy 802 Non-Compliance Human Subjects Research found at: <https://irbo.nih.gov/confluence/pages/viewpage.action?pageId=36241835#Policies&Guidance-800Series-ComplianceandResearchEventReportingRequirements>.

Note: Only IND Safety Reports that meet the definition of an unanticipated problem will need to be reported per these policies.

7.2.2 IRB Requirements for PI Reporting at Continuing Review

Please refer to the reporting requirements in Policy 801: Reporting Research Events found at <https://irbo.nih.gov/confluence/pages/viewpage.action?pageId=36241835#Policies&Guidance-800Series-ComplianceandResearchEventReportingRequirements>.

7.3 NCI CLINICAL DIRECTOR REPORTING

Problems expeditiously reported to the OHSRP in the NIH eIRB system will also be reported to the NCI Clinical Director/designee; therefore a separate submission for these reports is not necessary.

In addition to those reports, deaths not reported to the OHSRP/IRB that occur within 30 days after receiving a research intervention should be reported via email unless they are due to progressive disease.

To report these deaths, please send an email describing the circumstances of the death to [contact] within one business day of learning of the death.

7.4 NIH REQUIRED DATA AND SAFETY MONITORING PLAN

7.4.1 Principal Investigator/Research Team

The clinical research team will meet on a regular basis (approximately weekly) when participants are being actively treated on the trial to discuss each participant. Decisions about dose level enrollment and dose escalation if applicable will be made based on the toxicity data from prior participants.

All data will be collected in a timely manner and reviewed by the principal investigator or a lead associate investigator. Events meeting requirements for expedited reporting as described in Section [7.2.1](#) will be submitted within the appropriate timelines.

The principal investigator will review adverse event and response data on each participant to ensure safety and data accuracy. The principal investigator will personally conduct or supervise

the investigation and provide appropriate delegation of responsibilities to other members of the research staff.

7.4.2 Data Safety Monitoring Board (DSMB)

The DSMB is an independent group of at least 3 experts that monitors participant safety and advises The Sponsor. DSMB members will be separate and independent of study staff participating in this trial and should not have scientific, financial, or other conflicts of interest related to this trial. The DSMB will consist of members with appropriate expertise to contribute to the interpretation of data from this trial. A quorum will consist of a simple majority.

The DSMB will review cumulative safety data and interim analysis data (see Section [10.4.5](#)) generated in review timeframe from this trial at least annually.

The DSMB will meet when trial halting criteria (see Section [3.2](#)) are met, or as requested by the sponsor or PI.

The DSMB will have a final review meeting at the end of the study.

Procedures for DSMB reviews/meetings will be defined in the DSMB charter. The DSMB will review applicable data, including, but not limited to, enrollment, demographics, dosing data, clinical laboratory data, and safety data, at scheduled timepoints during this trial as defined in the DSMB charter. The DSMB will review blinded aggregate data in the open session of the DSMB meetings.

Additional data may be requested by the DSMB, and interim statistical reports may be generated as deemed necessary and appropriate by the Sponsor. As an outcome of each review/meeting, the DSMB will make a recommendation as to the advisability of proceeding with study product administration, and to continue, modify, or terminate this trial.

8 SPONSOR PROTOCOL / SAFETY REPORTING

8.1 DEFINITIONS

8.1.1 Adverse Event

Any untoward medical occurrence in a participant or clinical investigation subject administered a pharmaceutical product and which does not necessarily have a causal relationship with this treatment. An adverse event (AE) can therefore be any unfavorable and unintended sign (including an abnormal laboratory finding), symptom, or disease temporally associated with the use of a medicinal (investigational) product, whether or not related to the medicinal (investigational) product (ICH E6 (R2)).

8.1.2 Serious Adverse Event (SAE)

An adverse event or suspected adverse reaction is considered serious if in the view of the investigator or the sponsor, it results in any of the following:

- Death;
- A life-threatening adverse event (see Section [8.1.3](#));
- In participant hospitalization or prolongation of existing hospitalization;

- A hospitalization/admission that is pre-planned (i.e., elective or scheduled surgery arranged prior to the start of the study), a planned hospitalization for pre-existing condition, or a procedure required by the protocol, without a serious deterioration in health, is not considered a serious adverse event.
- A hospitalization/admission that is solely driven by non-medical reasons (e.g., hospitalization for participant convenience) is not considered a serious adverse event.
- Emergency room visits or stays in observation units that do not result in admission to the hospital would not be considered a serious adverse event. The reason for seeking medical care should be evaluated for meeting one of the other serious criteria.
- Persistent or significant incapacity or substantial disruption of the ability to conduct normal life functions;
- A congenital anomaly/birth defect;
- Important medical events that may not result in death, be life-threatening, or require hospitalization may be considered a serious adverse drug experience when, based upon appropriate medical judgment, they may jeopardize the participant or subject and may require medical or surgical intervention to prevent one of the outcomes listed in this definition.

8.1.3 Life-threatening

An adverse event or suspected adverse reaction is considered “life-threatening” if, in the view of either the investigator or sponsor, its occurrence places the participant or subject at immediate risk of death. It does not include an adverse event or suspected adverse reaction that, had it occurred in a more severe form, might have caused death (21CFR312.32).

8.1.4 Severity

The severity of each Adverse Event will be assessed utilizing the CTCAE version 5.0.

8.1.5 Relationship to Study Product

All AEs will have their relationship to study product assessed using the terms: related or not related.

- Related – There is a reasonable possibility that the study product caused the adverse event. Reasonable possibility means that there is evidence to suggest a causal relationship between the study product and the adverse event.
- Not Related – There is not a reasonable possibility that the administration of the study product caused the event.

8.1.6 Adverse Events of Special Interest (AESI)

An adverse event of special interest (AESI) is one of scientific and medical interest specific to understanding of the Investigational Product(s) and may require close monitoring and rapid communication by the investigator to the sponsor. An AESI may be serious or non-serious. The rapid reporting of AESIs allows ongoing surveillance of these events to characterize and understand them in association with the use of these investigational products.

Only AESIs that match the definition of SAE will be reported as other SAEs within 7 days from the knowledge of event. Other non-SAE AESIs should not be reported to OSRO but only collected in the clinical database.

The adverse events related to following, regardless of site, will be collected as an AESI to enable evaluation of potential risk factors, such as site/past radiation/associated infection at site/recent instrumentation and other variables such as time to onset, exposure history, grade of bleeding, anatomical sites, etc. can be collected.

- Mucosal bleeding
- Cutaneous lesions possibly due to TGF-beta

8.2 ASSESSMENT OF SAFETY EVENTS

AE information collected will include event description, date of onset, assessment of severity and relationship to study product and alternate etiology (if not related to study product), date of resolution of the event, seriousness and outcome. The assessment of severity and relationship to the study product will be done only by those with the training and authority to make a diagnosis and listed on the Form FDA 1572 as the site principal investigator or sub-investigator. AEs occurring during the collection and reporting period will be documented appropriately regardless of relationship. AEs will be followed through resolution.

SAEs will be:

- Assessed for severity and relationship to study product and alternate etiology (if not related to study product) by a licensed study physician listed on the Form FDA 1572 as the site principal investigator or sub-investigator.
- Recorded on the appropriate SAE report form, the medical record and captured in the clinical database.
- Followed through resolution by a licensed study physician listed on the Form FDA 1572 as the site principal investigator or sub-investigator.

For timeframe of recording adverse events, please refer to Section [6.1](#).

8.3 REPORTING OF SERIOUS ADVERSE EVENTS

Any AE that meets protocol-defined serious criteria or meets the definition of Adverse Event of Special Interest that require expedited reporting must be submitted immediately (within 24 hours of awareness) to OSRO Safety using the CCR SAE report form.

All SAE reporting must include the elements described in Section [8.2](#).

SAE reports will be submitted to the Center for Cancer Research (CCR) at: [contact] and to the CCR PI and study coordinator. CCR SAE report form and instructions can be found at: <https://ccrod.cancer.gov/confluence/display/CCRCRO/Forms+and+Instructions>

Following the assessment of the SAE by OSRO, other supporting documentation of the event may be requested by the OSRO Safety and should be provided as soon as possible.

8.4 WAIVER OF EXPEDITED REPORTING TO CCR

As overall survival, which includes death or hospitalization due to disease progression are part of the study objectives, and captured as an endpoint in this study, they will not be reported in expedited manner to the sponsor. However, if there is evidence suggesting a causal relationship between the study drug and the event, report the event in an expedited manner according to Section [8.3](#).

Hospitalization that is deemed to be due to disease progression, and not attributable to the intervention will not be reported as an SAE. The event, and the assessment that it was caused by disease progression will be documented in the medical records. The causality assessment of hospitalization will be re-evaluated any time when new information is received. If the causality assessment changes from disease progression to related to the study intervention, SAE report will be sent to the Sponsor in an expedited manner according to Section [8.3](#). If there is any uncertainty whether the intervention is a contributing factor to the event, the event should be reported as AE or SAE as appropriate.

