8.7 REGULATORY REPORTING FOR STUDIES CONDUCTED UNDER CCR-SPONSORED IND

Following notification from the investigator, CCR, the IND sponsor, will report any suspected adverse reaction that is both serious and unexpected. CCR will report an AE as a suspected adverse

reaction only if there is evidence to suggest a causal relationship between the study product and the adverse event. CCR will notify FDA and all participating investigators (i.e., all investigators to whom the sponsor is providing drug under its INDs or under any investigator's IND) in an IND safety report of potential serious risks from clinical trials or any other source, as soon as possible, in accordance to 21 CFR Part 312.32.

All serious events will be reported to the FDA at least annually in a summary format.

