10.4.2 Analysis of the Secondary Endpoint(s)

PFS will be determined using the Kaplan-Meier method and will be reported along with 95% confidence intervals. PFS will be defined as the time from the date of first treatment to the date of disease progression or death (any cause) whichever occurs first. Subjects who do not have disease progression or have not died at the end of follow up will be censored at the last known date the subject was progression free.

OS will be evaluated using Kaplan-Meier methods. OS will be defined as the time from the date of first treatment to the date of death (any cause). Subjects who are alive at the end of follow up will be censored at the last known date alive.

Duration of Response: The duration of overall response is measured from the time measurement criteria are met for CR or PR (whichever is first recorded) until the first date that PD or death is objectively documented and is evaluated using the Kaplan-Meier method. Analysis of safety and tolerability is as described in the Section **10.4.3**.

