12.5 RISK/BENEFIT ASSESSMENT

12.5.1 Known Potential Risks

12.5.1.1 Potential Risks Associated with Bintrafusp alfa

Potential adverse reactions attributable to the administration of the study drugs utilized in this trial are discussed in Section [14.1.2](#). Risks include the possible occurrence of any of a range of side effects which are listed in the Consent Document or this protocol document. Frequent monitoring for adverse effects will help to minimize the risks associated with administration of the study agents.

Participants may be harmed from being in this study by toxicity due to the drug or combination of drugs given during this study. M7824 is similar to immune check point inhibitors. There are preliminary data to suggest that not all patients benefit from immune check point inhibitors nor M7824. Additionally, there are preliminary data to suggest that an unexpectedly rapid progression of disease occurs in some patients receiving immunotherapy such as immune checkpoint inhibitors.

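### Section 8.4 takes progression-attributed hospitalisations out of SAE reporting on the ground that overall survival captures them; it does not, and the rule conflicts with sections 8.1.2, 8.2 and 8.7

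*Combined protocol and SAP*

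**What the plan says.** Section 8.4, on waiving expedited reporting to the sponsor, gives as its reason that "overall survival, which includes death or hospitalization due to disease progression are part of the study objectives, and captured as an endpoint". It keeps a first exception: "However, if there is evidence suggesting a causal relationship between the study drug and the event, report the event in an expedited manner".

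Its second paragraph is a separate and wider rule: "Hospitalization that is deemed to be due to disease progression, and not attributable to the intervention will not be reported as an SAE". On where such an event is kept, it says: "The event, and the assessment that it was caused by disease progression will be documented in the medical records". It then requires causality to be reconsidered when new information arrives. It also requires an AE or SAE report if there is any uncertainty about a contribution from the drug.

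Elsewhere:
- **10.4.2:** "OS will be defined as the time from the date of first treatment to the date of death (any cause"). PFS in the same section is time to progression or death.
- **8.7:** "All serious events will be reported to the FDA at least annually in a summary format".
- **12.5.1.1:** the risk section states that "there are preliminary data to suggest that an unexpectedly rapid progression of disease occurs in some patients receiving immunotherapy".
- **7.3:** deaths within 30 days of a research intervention that have not already gone to the IRB office "should be reported via email unless they are due to progressive disease".

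**The concern.** A waiver of this kind is reasonable when the event is collected elsewhere as an endpoint. For deaths that is true. For hospitalisations it is not, so the stated reason does not support the rule. The rule also does more than relax a reporting clock, because it changes what counts as an SAE.

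Safety and tolerability is a secondary objective, and the SAE table in 10.4.3 is one of its main outputs. Under 8.4, whether an admission appears in that table depends on one investigator's judgement that it was due to progression. In an open-label single-arm trial there is no control group against which to check that judgement. The protocol also names a risk, unexpectedly rapid progression, that in an individual patient looks the same as natural progression.

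**Working it through.** The point is mainly textual, and the plan has no figure of its own to reproduce.

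**Step 1. Does any endpoint count hospitalisation?**
- Primary: objective response rate (10.1.1). No.
- Secondary efficacy: PFS (progression or death), duration of response (response to progression or death) and OS (death), all in 10.4.2. No.
- Safety (10.4.3): AEs and SAEs. Yes, but only if the admission is reported as an SAE, which 8.4 rules out.

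**Step 2. Is 8.4 consistent with the other safety sections?**

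| Section | What it requires | Fit with 8.4 |
|---|---|---|
| 8.1.2 | Inpatient hospitalisation makes an event serious. The exceptions are pre-planned or protocol-required admissions, non-medical admissions, and emergency or observation stays without admission | Progression is not among the exceptions |
| 8.2 | SAEs go to the SAE form, the medical record and the clinical database | 8.4 names only the medical record |
| 8.7 | All serious events go into the annual FDA summary | Serious under 8.1.2, but not reported as an SAE under 8.4 |
| 10.4.3 | SAEs are tabulated | An event not reported as an SAE is not in that table |

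**Step 3. Exactly what is removed?** Only admissions judged both due to progression and not attributable to the drug. Deaths due to progression lose expedited timing only. They stay serious under 8.1.2 and are counted in OS.

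**Step 4. What else could show rapid progression?** PFS dates, early deaths in OS, imaging every 8 weeks, and the accrual halt in section 3.2. The halt calls a DSMB review if more than 85% of participants have progressed within 6 months, checked once the sixth participant reaches 6 months. Assume the denominator is exactly 6. Then 5/6 = 83.3% does not exceed 85%, so all six must have progressed, and the trigger probability is p^6 for a true 6-month progression rate p:

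| Assumed p | p^6 |
|---|---|
| 50% | 1.6% |
| 70% | 11.8% |
| 85% | 37.7% |
| 95% | 73.5% |

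This route exists but is insensitive, and it does not separate progression in the first weeks from progression at month 5. Section 8.4 requires no imaging before an admission is put down to progression, so an admission before the first restaging scan may precede any dated progression.

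**Step 5. Scale.** No hospitalisation rate is given. Section 10.3 reports the two cohorts separately. Taking 21 treated checkpoint-naïve and 8 treated checkpoint-resistant participants, and ignoring the up to 3 extra places for inevaluable participants, each participant whose only SAE is omitted lowers the reported proportion by 1/21 = 4.8 percentage points or 1/8 = 12.5 percentage points respectively.

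**The case against.** The strongest reply is that 8.4 is narrow and has safeguards. It covers only admissions judged unrelated to the drug. Evidence of causality restores expedited reporting, any uncertainty requires an AE or SAE report, and attributions are reopened on new information. The team discusses each participant about weekly (7.4.1), and the DSMB may ask for more data (7.4.2). All of this stands and limits the consequence. It does not repair the false rationale or the conflicts with 8.1.2, 8.2 and 8.7. The uncertainty clause also operates only when the investigator doubts the attribution.

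A reader might infer four stronger things that the documents do not support:
- **These events vanish from the safety data.** Section 8.2 still requires AEs to be documented regardless of relationship. Whether the underlying event stays in the database as a non-serious AE is not stated. That is a gap, not an exclusion.
- **Rapid progression cannot come to light.** PFS, OS, the 3.2 halt and the clauses of 8.4 itself all remain. The 30-day exemption in 7.3 concerns an e-mail route to the Clinical Director and does not remove deaths from the safety record.
- **The pooled data in 14.1.2 size the problem.** There, 79 of 630 participants had fatal TEAEs and 7 deaths were called treatment-related. The other 72 were not called treatment-related, which is not the same as attributed to progression. They are also deaths, not admissions.
- **Bleeding admissions would be lost as progression.** Nothing in the text shows this, and 8.1.6 collects mucosal bleeding as an event of special interest even when it is not serious.

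**Conclusion.** The point holds in a limited form. The reason given in 8.4 contradicts 10.4.2, and the exclusion of progression-attributed admissions from SAE reporting contradicts the protocol's own definition, recording rule and annual-summary commitment. The SAE table would be incomplete by an amount that depends on attribution, and detection of rapid progression is weakened rather than lost. The number of omitted events is unknown; the per-participant effect in step 5 assumes full accrual and that the participant has no other SAE. The conclusion also rests on reading 10.4.3 as tabulating only events reported as SAEs. The response endpoint, the two-stage design and the sample size are untouched. The change is worth making because it is cheap and bears on a secondary objective.

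**What to change.** In 8.4:
1. Delete the reference to hospitalisation from the sentence about overall survival.
2. Limit the waiver to expedited timing, and remove the statement that these admissions are not SAEs.
3. Require every progression-attributed hospitalisation in the AE window (first dose to 28 days after the last, per 6.1) to be entered in the clinical database as a non-expedited SAE, with its attribution and its date relative to first dose.

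State that these entries are included in the 10.4.3 tables, the 8.7 annual summary and the cumulative safety data that the DSMB already reviews under 7.4.2. A table that splits SAEs by attribution would let readers see both totals. A separate DSMB listing is optional.

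The cost is a few sentences of amendment, a few more database entries in a trial capped at 32 participants, and a slightly higher reported SAE rate. Expedited reporting workload does not change.
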